5.4.5 Crude incidence and related risk estimates

5.4.5.1 Crude incidence and 100*(1- α)% confidence interval

For n subjects, each at risk to experience a certain event with probability π , the crude incidence is estimated as $p=x/n$, where x is the number of subjects with the event.

Absolute and relative frequencies will be displayed as well as 95% confidence interval for the relative frequency based on the score method including continuity correction ([Newcombe 1998](#)).

With z as $(1-\alpha/2)$ -quantile of the standard normal distribution (SAS: $z=PROBIT(1-\alpha/2)$), n as total number of subjects (i.e. number of subjects in the denominator), and p as estimated crude incidence (number of subjects with event / n) it is $q = 1 - p$.

Then the lower limit is

$$L = \max \left(0, \frac{2np + z^2 - 1 - z\sqrt{z^2 - 2 - \frac{1}{n} + 4p(nq+1)}}{2(n+z^2)} \right)$$

and the upper limit is

$$U = \min \left(1, \frac{2np + z^2 + 1 + z\sqrt{z^2 + 2 - \frac{1}{n} + 4p(nq-1)}}{2(n+z^2)} \right).$$

Note: if $p = 0$ then $L = 0$ and if $p = 1$ then $U = 1$.

If appropriate, an exact $100*(1-\alpha)\%$ confidence interval ([Clopper-Pearson 1934](#)) will be obtained by using the SAS procedure PROC FREQ with the EXACT BINOMIAL statement. However, the confidence interval derived via the score method including continuity correction will be the default in safety analyses.

5.4.5.2 Relative risk and 100*(1- α)% confidence interval

For an investigational drug group with n_1 subjects at risk, independent from the control group (e.g., placebo or comparator) with n_0 subjects at risk, of whom x_1 and x_0 experience a certain event with probability π_1 and π_0 respectively, the relative risk is estimated as p_1/p_0 with $p_1=x_1/n_1$ and $p_0=x_0/n_0$.

An asymptotic $100*(1-\alpha)\%$ confidence interval on the relative risk will be based on the back-transformed large sample confidence limits on the log-transformed relative risk estimate which are obtained by application of the delta-method and Slutsky's theorem (Lachin 2000). The SAS procedure PROC FREQ with option RELRISK in the TABLES statement will be used to provide the asymptotic $100*(1-\alpha)\%$ confidence interval on the relative risk. The estimate is not computed if either x_1 or x_0 equals 0. In this case, or if the crude incidences are low in both groups, the relative risk will be approximated by the odds ratio for which an exact confidence interval will be obtained as specified in [Section 5.4.6.3](#). If the relative risk is not well approximated by the odds ratio but asymptotic normality is questionable, STATAACT will be used.

5.4.5.3 Odds ratio and $100*(1-\alpha)\%$ confidence interval

For an investigational drug group with n_1 subjects at risk, independent from the control group (e.g. placebo) with n_0 subjects at risk, of whom x_1 and x_0 experience a certain event with probability π_1 and π_0 respectively, the odds ratio is estimated as

$$\frac{p_1 / (1 - p_1)}{p_0 / (1 - p_0)}$$
 with $p_1 = x_1/n_1$ and $p_0 = x_0/n_0$. A conditional exact $100*(1-\alpha)\%$ confidence interval

will be obtained by using the SAS procedure PROC FREQ with statement EXACT OR.

5.4.5.4 Risk difference and $100*(1-\alpha)\%$ confidence interval

For an investigational drug group with n_1 subjects at risk, independent from the control group (e.g., placebo or comparator) with n_0 subjects at risk, of whom x_1 and x_0 experience a certain event, the risk difference is estimated as $p_1 - p_0$ with $p_1 = x_1/n_1$ and $p_0 = x_0/n_0$.

Exact unconditional confidence limits for the risk difference will be obtained with SAS procedure PROC FREQ and option RISKDIFF in the TABLES statement, specifying the RISKDIFF option also in the EXACT statement.

5.4.6 Exposure adjusted incidence rate and related risk estimates

5.4.6.1 Exposure adjusted incidence rate and $100*(1-\alpha)\%$ confidence interval

It will be assumed that for each of n subjects in a clinical trial the time t_j ($j=1, \dots, n$) to the first occurrence of a certain treatment emergent event is observed, or if the event was not experienced, the (censored) time to the end of the observation period or last dose plus 84 days whichever occur earlier. The sequence of first occurrences of an event will be modeled to follow approximately a Poisson process with constant intensity θ . The rate parameter θ will be

estimated as $\lambda = D/T$, where $T = \sum_{j=1}^n t_j$ and D is the number of subjects with at least one event.

Conditionally on T , an exact $100*(1-\alpha)\%$ confidence interval for a Poisson variable with parameter θT and observed value D can be obtained based on (Garwood, 1936), from which an exact $100*(1-\alpha)\%$ confidence interval for D/T will be derived as follows (Sahai, 1993; Ulm, 1990):

Lower confidence limit $L = \frac{0.5c_{\alpha/2,2D}}{T}$ for $D>0$, 0 otherwise,

Upper confidence limit $U = \frac{0.5c_{1-\alpha/2,2D+2}}{T}$

where $c_{\alpha,k}$ is the α th quantile of the Chi-square distribution with k degrees of freedom.

5.4.6.2 Exposure-adjusted event rate and 100*(1- α)% confidence interval

For each of n subjects t_j ($j=1, \dots, n$) specifies the exposure time. The number of occurrences of a treatment emergent event will be modeled to follow approximately a Poisson process with constant intensity θ . The rate parameter θ will be estimated as $\lambda=D/T$, where $T = \sum_{j=1}^n t_j$ and D is the number of events (episodes). Conditionally on T , an exact 100*(1- α)% confidence interval for a Poisson variable with parameter θT and observed value D can be obtained based on (Garwood, 1936), from which an exact 100*(1- α)% confidence interval for D/T will be derived as follows (Sahai, 1993; Ulm, 1990):

Lower confidence limit $L = \frac{0.5c_{\alpha/2,2D}}{T}$ for $D>0$, 0 otherwise,

Upper confidence limit $U = \frac{0.5c_{1-\alpha/2,2D+2}}{T}$

where $c_{\alpha,k}$ is the α th quantile of the Chi-square distribution with k degrees of freedom.

5.5 Rule of exclusion criteria of analysis sets

Protocol deviations for exclusion from analysis sets are defined in [Table 5-1](#).

Table 5-1 Subject classification rules

Analysis set	PD Categories Codes that cause subject to be excluded	Non-PD criteria that cause a subject to be excluded
Randomization set	NA	Misrandomized subject
FAS (Full Analysis Set)	DVSPID:INCL01, OTH17; OTH12	Misrandomized subject
Safety	DVSPID: INCL01, OTH17; OTH12	Subjects who did not take any study treatment

OTH17: Patient was rescreened, or new/updated ICF available but patient did not sign a new ICF

OTH12: Severe ICH-GCP non-compliance of study site

5.6 Clinician reported outcomes

5.6.1 Usability and hazard assessment of the 2 mL auto-injector

The goal is to measure and evaluate the usability of the auto-injector during observed use. During the first 2mL self-injection at the respective visits (Randomization and Week 1), site staff will observe and complete the self-injection assessment checklist ([Table 5-2](#)) to assess the ability to follow the instructions for use (IFU). The possible hazard checklist ([Table 5-3](#)) will be assessed for the 2mL self-injection at each of the two visits.

Primary usability assessment:

- Assessment of successful self-administration by the subject at Week 1. Successful self-injection is achieved when the subject performs all required steps effectively and safely to deliver the correct dose from the device at the correct injection site. The sequence of user steps (as per IFU) that are minimally required are P7, P9, P10 and P11 ([Table 5-2](#)), these 6 critical steps will be used to define successful administration. The general passing usability goal for ‘successful use’ task completion will be defined as $\geq 90\%$ pass rate following these steps.

Secondary usability assessment:

- Assessment of subject use errors that occur during the First Use at Randomization (after initial training) and repeated self-injection at Week 1 (without retraining).
- Assessment of successful First Use by subject after initial training (at Randomization), for subjects who successfully perform the self-injection as defined above for the primary usability assessment (i.e. P7, P9, P10 and P11).

Table 5-2 Self injection assessment checklist (auto-injector)

No.	IFU indicated steps	Required to be completed for successful administration
P1	Washed hands with soap and water	No
P2	Cleaned the injection site	No
P3	Removed the auto-injector from the outer box	No
P4	Checked expiration date on auto-injector label	No
P5	Inspected the auto-injector for damage	No
P6	Inspected liquid for brown discoloration or particles	No
P7	Removed cap from auto-injector	Yes
P8	Discarded cap	No
P9	Hold the auto-injector at correct angle to the injection site	Yes
P10	Press the auto-injector firmly against the skin to trigger the injection (1 st Click), and keep holding the auto-injector firmly against the skin	Yes
P11	Wait until the injection is complete, confirmed by the 2 nd “click” and/or a check that the yellow indicator fills the window	Yes

No.	IFU indicated steps	Required to be completed for successful administration
P12	The auto-injector can now be removed	No
P13	Check again that the yellow indicator fills the window	No
P14	Disposed used auto-injector in a sharps container	No

Table 5-3 Possible hazard assessment checklist

No.	Possible hazard assessment checklist
H1	Was there a needle stick in a critical area (e.g. eye, carotid artery)?
H2	Was there a needle stick in a non-critical area? ¹
H3	Was any part of the device swallowed? If yes, please specify.
H4	Was an immediate-type allergic reaction noticed to device material?
H5	Was increased pain noticed by the patient due to a bent needle?
H6	Was the breakage of the device observed? ²
H7	Was swallowing of material debris observed?
H8	Was any other problem observed? ³
H9	Was less than the full dose administered? ⁴

The following potential hazards from the Hazards Identified List ([AIN457_HID_Delta225-01]) have not been included as not being observable during self-injection observation: microbiological contamination, wrong drug, transfer of transmissible diseases.

¹ Excluding the actual injection into the appropriate injection site of the body

² If yes, then it is to be specified under which circumstances breakage occurred and which parts were affected, as well any additional problems (e.g. injuries) due to the breakage are to be described.

³ If yes, then it is to be specified. Possible events might include: irritated skin; drug too cold when injected; the drug or device upon visual inspection appeared unsuitable for injection; intradermal instead of subcutaneous injection; and other events.

⁴ If yes, then it is to be specified why, e.g. leakage from injection site, early removal.

5.7 Patient reported outcomes

The impact of psoriasis on various aspects of subjects' health-related quality of life will be assessed by the DLQI in this trial.

5.7.1 Dermatology Life Quality Index (DLQI)

The DLQI is a 10-item general dermatology disability index designed to assess Health-related quality of life in adult subjects with skin diseases (e.g. psoriasis). The measure is self-administered and includes six domains of symptoms and feelings, daily activities, leisure, work and school, personal relationships and treatment.

The scoring of each question is as follows:

- Very much: Scored 3
- A lot: Scored 2
- A little: Scored 1

- Not at all: Scored 0
- Not relevant: Scored 0
- Question unanswered: Scored 0
- Question 7: "prevented work or studying": Scored 3

The DLQI total score will be calculated by summing the score of each question resulting in a maximum of 30 and a minimum of 0. The higher the score, the more Quality of Life is impaired.

Meaning of DLQI Scores:

- 0-1= no effect at all on subject's life
- 2-5= small effect on subject's life
- 6-10= moderate effect on subject's life
- 11-20= very large effect on subject's life
- 21-30= extremely large effect on subject's life

The DLQI will be analyzed under six headings as follows:

- Symptoms and feelings: questions 1 and 2, score maximum 6
- Daily activities: questions 3 and 4, score maximum 6
- Leisure: questions 5 and 6, score maximum 6
- Work and school : question 7, score maximum 3
- Personal relationships: questions 8 and 9: score maximum 6
- Treatment: question 10, score maximum 3

Interpretation of incorrectly completed questionnaires:

There is a very high success rate of accurate completion of the DLQI. However, sometimes subjects do make mistakes.

1. If one question is left unanswered this is scored 0.
2. If two or more questions are left unanswered the questionnaire will not be scored.
3. If question 7 is answered 'yes' this will be scored 3. If question 7 will be answered 'no' or 'not relevant' but then either 'a lot' or 'a little' is ticked this will then be scored 2 or 1, respectively.
4. If two or more response options are ticked, the response option with the highest score will be recorded.
5. If there is a response between two tick boxes, the lower of the two score options will be recorded.
6. If one item is missing from a two- item subscale that subscale will not be scored.

Handling of missing values:

- If there is only one missing score per visit, it will be imputed with 0, and then the subscale including this item and the total score are derived accordingly.
- If there are two or more missing scores per visit, LOCF will be applied to the individual question scores, subscale scores, and total score, separately (i.e. LOCF is NOT applied to the 10 individual question scores for further derivation of the 6 subscale scores and 1 total score).

Of note, in situations where subjects responded to more questions than what was expected or required, the “most severe” answer was entered into the WriteResult (vendor for PRO data) database. In most cases the Self-Evident Corrections (SECs) were defined correctly, however, the SEC regarding question 7A/7B was not designed to select the “most severe” answer. This was confirmed with Novartis HEOR and communicated to the AIN team.

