8.5.1.1 Patient Reported Outcomes (PRO)

All subjects will complete the PRO questions via an electronic tablet. The subject should be given sufficient space and time to complete the questionnaires. In case of any issues with tablet use, which cannot be resolved within the visit time window subject can complete PRO questions on paper form. If subject experiences any difficulties with submission after they complete the PROs, the study staff should assist with submitting the PRO responses. Attempts should be made to collect responses to all PROs for all subjects, including from those who prematurely discontinue prior to the study evaluation completion visit, however, if subjects refuse to complete PROs, this should be documented in study source records. Subject’s refusal to complete study PROs are not protocol deviations.

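### SAP 5.7.1 notes that the vendor's correction for DLQI question 7 was not designed to keep the most severe answer, yet states no repair; contradictory 7A/7B responses can be scored 1 to 3 points too low

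*SAP*

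**What the plan says.** SAP 5.7.1 lists rules for incorrectly completed DLQI questionnaires. Item 3 covers question 7: "If question 7 is answered 'yes' this will be scored 3". Under the same item, a 7A answer of 'no' or 'not relevant' followed by 'a lot' or 'a little' scores 2 or 1. Item 4 covers multiple ticks: "If two or more response options are ticked, the response option with the highest score will be recorded".

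The section closes with a note on subjects who answered more questions than required. For them the most severe answer was entered in the vendor's database. The note continues: "In most cases the Self-Evident Corrections (SECs) were defined correctly"; "however, the SEC regarding question 7A/7B was not designed to select the" most severe answer. The only follow-up given is: "This was confirmed with Novartis HEOR and communicated to the AIN team".

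Question 7 counts in three places:

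- It is the whole of one subscale: "Work and school : question 7, score maximum 3".
- It enters the total: "The DLQI total score will be calculated by summing the score of each question resulting in a maximum of 30 and a minimum of 0".
- Through the total it enters DLQI 0 or 1 achievement, which SAP Table 1-1 lists as secondary.

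Protocol 8.5.1.1 has subjects answer on a tablet. If a tablet problem cannot be resolved within the visit window, the "subject can complete PRO questions on paper form".

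**The concern.** The SAP gives a scoring rule and then reports that the data source was not built to follow it for one item. The correction is described as fixing what was entered in the vendor's database, which comes before any SAP scoring. If only the corrected value reaches the sponsor, items 3 and 4 have nothing left to act on.

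What is at stake is the work and school score, the total score and DLQI 0/1. SAP Section 4 removes the Van Elteren test and the Hodges-Lehmann estimates for the total score. That leaves Fisher's exact test on DLQI 0/1 (SAP 2.12) as the only between-group DLQI test still specified. DLQI 0/1 is a threshold at the bottom of the scale, so one under-scored item can change a subject's classification. SAP 2.12 also carries DLQI values forward, so an under-scored post-baseline value can reappear at later visits.

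**Working it through.** **1. The SAP's own range.** Ten items with a maximum of 3 give 10 × 3 = 30. The subscale maxima in SAP 5.7.1 give 6 + 6 + 6 + 3 + 6 + 3 = 30. Both match the stated maximum. Question 7 carries up to 3 of those 30 points.

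**2. Which responses are affected.** In Protocol Appendix 5, part 7B is asked when 7A is 'no'. Answering both parts after 'no' is therefore the normal route and needs no correction. Over-answering means a 7B answer given together with 7A 'yes' or 'not relevant'.

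**3. Size per questionnaire.** Scores are 7A: yes = 3, not relevant = 0; 7B: a lot = 2, a little = 1, not at all = 0. The SAP score is the higher of the two (items 3 and 4). The note does not say which answer the correction keeps, so the worst case assumes that the lower of the two was stored. Let *r* be the sum of the other nine items (0 to 27). A false DLQI 0/1 needs *r* + SAP score > 1 and *r* + stored score ≤ 1.

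| 7A + 7B | SAP score | Lower answer kept | Too low by | *r* giving a false 0/1 | True total → recorded total |
|---|---|---|---|---|---|
| yes + a lot | 3 | 2 | 1 | none | – |
| yes + a little | 3 | 1 | 2 | 0 | 3 → 1 |
| yes + not at all | 3 | 0 | 3 | 0 or 1 | 3 or 4 → 0 or 1 |
| not relevant + a lot | 2 | 0 | 2 | 0 or 1 | 2 or 3 → 0 or 1 |
| not relevant + a little | 1 | 0 | 1 | 1 | 2 → 1 |
| not relevant + not at all | 0 | 0 | 0 | none | – |

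Where there is an error it is 1 to 3 points downward. No pattern scores too high, because the SAP score is already the maximum of the answers given.

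**4. Size per group.** About 120 subjects at 2:2:1:1 give 120 × 2/6 = 40 on the auto-injector, 40 on the syringes, and 120 × (1 + 1)/6 = 40 on pooled placebo. One false DLQI 0/1 responder moves a group's rate by 1/40 = 2.5 percentage points. This is the unit of effect, not an estimate of it.

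**5. Direction for percentage change.** With baseline *B* and visit value *W*, the change is 100 × (*W* − *B*)/*B* = 100 × (*W*/*B* − 1). Under-scoring *W* by *d* lowers this by 100 × *d*/*B*, so improvement looks larger. Under-scoring *B* by *d* turns *W*/*B* into *W*/(*B* − *d*), which is larger when *W* > 0, so improvement looks smaller. The direction depends on which visit is affected.

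**6. Is a repair written elsewhere?** SAP 2.12 (patient-reported outcomes), Section 4 (changes to protocol analyses), 5.1.5 (other imputations) and the rest of 5.7.1 contain no re-derivation of question 7, vendor query, listing or sensitivity analysis for this fault.

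**The case against.** The strongest reply is that item 3 is already the repair: it scores 7A 'yes' as 3 and gives the scores for the other routes. If raw 7A and 7B both reach the sponsor, applying item 3 puts the score right. That stands as far as it goes, but the SAP does not say that both raw answers are transferred, and it places the correction at entry to the vendor's database. The reverse inference is no safer. A reader might conclude that the SAP analyses the vendor's value unchanged, but it does not say that either. The gap is silence on which value is used.

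Second, the note may not concern this trial. It is in the past tense, it refers to a programme-level team, and SAP Section 1 says the plan draws on a project master analysis plan. Collection here is by tablet, and the documents do not say whether the tablet blocks a 7B answer after 'yes'. This stands: the number of affected questionnaires may be zero.

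Third, a false DLQI 0/1 needs an unusual combination: a contradictory answer on question 7 and near-zero answers on the other nine items. This also stands, and it limits the likely size.

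Fourth, DLQI lies outside the controlled sequence of H1 and H2 followed by H3. That is correct, and no confirmatory conclusion depends on this point.

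**Conclusion.** The concern holds in a limited form. The SAP acknowledges a correction that conflicts with its own items 3 and 4 and states no repair. For contradictory 7A/7B responses the stored question 7 score can be 1 to 3 points too low and never too high, and a true total of 2 to 4 can be recorded as DLQI 0/1.

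This assumes that the correction stored one of the answers the subject gave, and that the raw pair is not otherwise used. The total effect cannot be computed, because the number of affected questionnaires is not given.

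Two stronger readings are tempting and are not supported:

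- A reader might infer a bias in favour of secukinumab. The trial is double-blind, and nothing suggests that the correction differed between arms. The documents do not show in which arm contradictory answers would be more common, and percentage change from baseline can move either way.
- A reader might infer that every questionnaire with both parts of question 7 answered is suspect. After 'no', answering both parts is what the form asks for.

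The co-primary endpoints and the key secondary endpoint are unaffected.

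**What to change.** Before database lock (for Week 12 data, the Week 16 lock), replace the closing note in SAP 5.7.1 with a derivation:

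- Obtain the raw 7A and 7B responses from the vendor.
- Derive question 7 from them under existing items 3 and 4: 'yes' = 3; 'no' or 'not relevant' with 'a lot' = 2, with 'a little' = 1; otherwise 0.
- List by arm and visit the questionnaires where this differs from the vendor's value. An empty list closes the matter.

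If the raw answers were not kept but the affected questionnaires can be identified, repeat DLQI 0/1 and the total score at Week 12 with question 7 set to the highest score compatible with items 3 and 4. A blanket score of 3 would be wrong wherever 7A is known to be 'not relevant', because item 3 then allows at most 2. If the affected questionnaires cannot be identified either, state this as a limitation of the DLQI results.

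If the note does not apply to this trial's tablet collection, say so and delete it.

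The cost is one vendor query, one derivation and one listing, plus one sensitivity analysis only if raw answers are missing. No new data collection is needed.

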5.7.2 Self-injection Assessment Questionnaire (SIAQ)

The Self-Injection Assessment Questionnaire (SIAQ) is a questionnaire to measure overall subject experience with subcutaneous self-injection, and to investigate its psychometric properties. The SIAQ is composed of two modules: the PRE-module and the POST-module. The PRE-module, which is completed at Randomization before the first self-injection (baseline), includes 7 items grouped into three domains: feelings about injections, self-confidence and satisfaction with self-injection. The POST-module, which is completed following the 2 mL AI and before the 1 mL PFS self-injections, includes several items addressing five principal domains: feelings about injections, self-confidence, injection-site reactions, ease of use, satisfaction plus a single item assessing self-image. Subjects will rate each item of the SIAQ on a 5-point semantic Likert-type scale ranging from 1 (worst experience) to 5 (best experience). Item score will be transformed to obtain a score ranging from 0 (worst experience) to 10 (best experience). The domain score will then be calculated as the mean of the item scores included in the domain.

Respondent rates each item of the PRE SIAQ and items 1-9 and 15-21 of the POST SIAQ on a 5-point semantic Likert-type scale, and items 10-14 of the POST SIAQ on a 6-point semantic Likert-type scale. For all items, a score of 1 corresponds to the subject’s worst experience and a score of 5 or 6 corresponds to the subject’s best experience.

The scoring of domains is performed in 2 steps:

1. The raw item scores ranging from 1 to 5 are transformed into scores ranging from 0 (worst experience) to 10 (best experience).
2. The transformed scores for items contributing to a domain are then averaged into a domain score ([Table 5-4](#)).

Table 5-4 Scoring of domains from raw item scores

	Items	Transformed item score	Domain score calculation	Domain score range
PRE-module domain				
FL	1-3	$((\text{raw score})-1)*2.5$	Average of transformed item scores	0-10
CO	4-6	$((\text{raw score})-1)*2.5$		
SA	7	$((\text{raw score})-1)*2.5$		

POST- module domain				
FL	1-3	$((\text{raw score})-1)*2.5$	Average of transformed item scores	0-10
IM	4	$((\text{raw score})-1)*2.5$		
CO	5-7	$((\text{raw score})-1)*2.5$		
RE	8-9	$((\text{raw score})-1)*2.5$		
EU	10-14	$((\text{raw score})-1)*2$		
SA	15-21	$((\text{raw score})-1)*2.5$		

FL=Feeling about injection, IM=Self-Image, CO=Self-Confidence, RE=Pain and skin reaction during or after the injection, EU=Ease of use of the self-injection device, SA=Satisfaction with Self-injection

PRE-module:

Item 1= In general, how afraid are you of needles?;
Item 2= In general, how afraid are you of having an injection?;
Item 3= How anxious do you feel about giving yourself an injection?;
Item 4= How confident are you about giving yourself an injection in the right way?;
Item 5= How confident are you about giving yourself an injection in a clean and sterile way?;
Item 6= How confident are you about giving yourself an injection safely?;
Item 7= Overall, how satisfied are you with your current way of taking your medication (self-injection)?

POST-module:

Item 1= In general, how afraid are you of needles?;
Item 2= In general, how afraid are you of having an injection?;
Item 3= How anxious do you feel about giving yourself an injection?;
Item 4= How embarrassed would you feel if someone saw you with the self-injection device?;
Item 5= How confident are you about giving yourself an injection in the right way?;
Item 6= How confident are you about giving yourself an injection in a clean and sterile way?;
Item 7= How confident are you about giving yourself an injection safely?;
Item 8a= During and/or after the injection, how bothered were you by: pain?;
Item 8b= During and/or after the injection, how bothered were you by: burning sensation?;
Item 8c= During and/or after the injection, how bothered were you by: cold sensation?;
Item 9a= During and/or after the injection, how bothered were you by: itching at the injection site?;
Item 9b= During and/or after the injection, how bothered were you by: redness at the injection site?;
Item 9c= During and/or after the injection, how bothered were you by: swelling at the injection site?;
Item 9d= During and/or after the injection, how bothered were you by: bruising at the injection site?;
Item 9e= During and/or after the injection, how bothered were you by: hardening at the injection site?;
Item 10= How difficult or easy was it to remove the cap?;
Item 11= How difficult or easy was it to depress the plunger or button on the device?;
Item 12= How difficult or easy was it to administer the injection without any help?;
Item 13= How difficult or easy was it to use the self-injection device?;
Item 14= How does the device fit in your hand?;
Item 15= How easy was it to give yourself an injection?;
